## 10.2 Intervals Between Visits

The intervals between screening and first administration may be  $3 \pm 2$  weeks, if necessary. A subject is considered enrolled when she receives the first Artesunate suppository at the scheduled Week 0 visit. After the first administration of Artesunate, the time window for each subject to complete 4 remaining daily doses of Artesunate suppositories may be between 4 days and 2 weeks (for example, to minimize potential wash-off of the treatment during a menstrual period). There will be a window of  $\pm 1$  week at weeks 2, 4, 6, 15, and post-operative visit, and  $\pm 2$  weeks at the week 28, and 41 visits.

### 10.3 Description of Study Visits

All clinically relevant data collected during the study procedures must be recorded first in the patient file. These data will then be transcribed into the CRF. All visits will be outpatient visits.

At the initial screening visit, in addition to undergoing a standard of care colposcopic evaluation, we will obtain cervical brush specimens for HPV typing, and peripheral blood specimens to determine HLA phenotype, HIV status, and immunologic studies. Subjects with biopsy-confirmed CIN2/3 will be enrolled into treatment cohorts as depicted in Table 4 below.

**Table 4 – Treatment Cohorts**

Cohort	Number of patients	Dose	Treatment cycles
I	3	50 mg	1 (5 days)
II	9	200 mg	1 (5 days)
III	9	200 mg	2 (5 days each)
IV	9	200 mg	3 (5 days each)

In cohort I, at the first study visit, the subjects will be given a total of five suppositories and applicators. The first suppository will be inserted in clinic, by the patient. Patients will be given diary cards, and will return 1-2 weeks after completing the regimen, for visual assessment of the cervicovaginal mucosa.

In cohorts II-IV, the first study visit will be the same as the first study visit for the run-in cohort. Subjects will return to clinic 1-2 weeks later for visual assessment of the cervicovaginal mucosa. At study week 2, patients enrolled in cohorts III and IV will undergo a visual assessment of their cervicovaginal mucosa and will be given an additional 5 suppositories and applicators. Patients enrolled in cohort III will return to clinic 1-2 weeks later for visual assessment of the cervicovaginal mucosa. At study week 4, subjects enrolled in cohort IV will undergo a visual assessment of their cervicovaginal mucosa, and will also be given five suppositories and applicators. At study week 6, **all subjects** will undergo an interval colposcopic assessment. If their lesions do not appear to be more severe than at study entry, they will return at study week 15. At study weeks 15 and 28, all subjects will undergo colposcopic evaluation. If there is any residual colposcopically abnormal tissue, it will be removed using standard excisional procedures. Peripheral blood and cervical brush specimens will be obtained at study entry, at week 5, at week 15, and at the follow-up visits: postoperative visit, and at weeks 28 and 41.

## **10.4 Examinations, Evaluations, and Procedures**

### **Vital signs**

Supine blood pressure and heart rate will be measured both prior to each procedure and drug administration. Additional investigation may be added at the discretion of the investigator.

### **Demographic data/medical history**

The patient's age, weight, height, and ethnicity will be ascertained at the screening visit. Information will be collected on the patient's past significant medical history including tobacco exposure, gynecologic and obstetric history including contraceptive use, total and current number of partners, and current medical status.

### **History of HPV disease**

The following information will be noted at the screening visit:

- month/year of detection of CIN lesions
- Details of previous therapies

### **Colposcopic examination**

Patients will undergo serial colposcopic examinations; at the screening visit, and at weeks 6, 15, 28. Exfoliated cell samples will be obtained using Digene swabs at the time of colposcopy, for HPV typing. Specimens for HPV genotyping will be processed by Quest Diagnostics, Nichols Institute. Specimens for quantitation of HPV viral load should be directed to the GYN biorepository, where they will be processed and cryopreserved for batch analysis. Swabs of cervical secretions will be banked in the tissue bank. Cervical lymphocyte samples will be processed directly.

### **LEEP/Cone Excisional Biopsy Procedure**

After week 15, if there is residual colposcopic disease, the affected area will be excised using standard LEEP or cold knife cone technique. The resection specimens will be taken fresh to surgical pathology. Frozen section will be performed to confirm the presence or absence of CIN2/3. The frozen section block will be banked at  $-70^{\circ}\text{C}$ , and a sliver of tissue immediately facing the frozen section will be reserved for isolation of immune cells. This will allow unhampered routine diagnostic ability as well as preserve tissue sections frozen for characterization of inflammatory cell infiltrates. Routinely processed formalin-fixed, paraffin-embedded sections will also be analyzed for the characterization and quantitation of tissue infiltrates.

### **Peripheral blood samples**

Blood will be drawn at various visits as noted in the protocol for analysis of various parameters and markers. The volume of blood will vary depending on the tests to be performed.

HLA typing: one 10 ml yellow top tube

Immunology samples: approximately 50 mls of blood drawn in green top (heparinized) tubes to the tissue core.

These specimens will be separated by standard Ficoll centrifugation, and the serum and PBLs aliquoted and banked at  $-70^{\circ}\text{C}$ .

### **Histologic response**

We will evaluate pathologic changes in diagnostic biopsy and post-suppository therapeutic resection material, on standard hematoxylin and eosin slides.

### **Urine sample**

A urine pregnancy test for HCG will be performed in patients of childbearing potential prior to each suppository administration.

### **HIV Testing**

HIV testing will be performed using standard JHH procedures including the JHH consent forms.

### **Immune Response**

We will assess peripheral blood specimens for immune responses to HPV antigens, using standard ELISA and ELISPOT assays. We will also perform quantitative digital image analyses of the tissue specimens obtained at diagnosis, and at week 15.

## **10.5 Compensation**

Study subjects will receive a total of \$200 if they participate in the entire study. A check will be mailed to their home within a month after each visit. Study subjects will receive \$20 for visits at weeks -3, 0, 2, 4, 5, 28, 41 and the postop visit and \$40 for the visit at week 15.

Upon completion of the postoperative visit, patients will have routine follow-up, including examinations at three-month intervals for the first year according to the standard of care.

## **11.0 STUDY DRUG AND ADMINISTRATION**

### **11.1 Description of Study Medication**

#### **Study Medication: Suppository Formulation of Artesunate**

[figure not shown]
## Drug Substance

Artesunate is a derivative of artemisinin which is the active principle of the Chinese medicinal herb *Artemisia annua*.

Nomenclature Artesunate, Artesunic acid

Chemical Name [3*R*, 5*aS*, 6*R*, 8*aS*, 9*R*, 10*S*, 12*R*, 12*aR*]-3,6,9-trimethyldecahydro-3,12-epoxyprano[4,3-*j*]-1,2-benzodioxepin-10-ol, hydrogen succinate;

CAS Reg. No. 88495-63-0

### General Properties

Molecular Formula C19H28O8

Molecular Weight 384.4 g/mol

Physical Description A fine, white crystalline powder

Solubility Very slightly in water; very soluble in dichloromethane; freely soluble in ethanol (~ 750 g/l) and acetone

Melting Point 132-135°C

Optical Rotation R; [α]D 20 °C = +2.5° to +3.5° in a 10mg/mL in dichloromethane

pH 3.5-4.5 in an aqueous suspension containing 10 mg/g

## Suppository Formulation

Artesunate suppositories will be produced under controlled environmental conditions as prescribed in USP Chapter 795. Artesunate will be added and dissolved into a molten fatty acid base. The mixture will then be transferred into disposable pre-formed suppository molds to cool into solid suppositories.

Clinical trial supplies will be produced by Buderer Drug Co. in Perrysburg, Ohio. Buderer maintains compliance with USP Chapter 795 (Pharmaceutical Compounding – Nonsterile Preparations) and USP Chapter 797 (Pharmaceutical Compounding – Sterile Preparations) which establish practice standards and outline the responsibility of the compounder, selection and appropriate sources of ingredients, quality control, and considerations regarding the stability of compounded preparations. Two additional USP informational chapters are in effect, including, USP Chapter 1075 – Good Compounding

Practices, and USP Chapter 1160 – Pharmaceutical Calculations in Prescription Compounding.

### **Packaging and Labeling**

Suppositories for dispensing will be packaged in standard prescription use plastic or cardboard containers. Proper labeling will be applied per state regulations.

### **Product Storage and Stability**

The suppositories may be stored at controlled room temperature. Suppositories for dispensing will be packaged in plastic or cardboard container, and kept in their plastic mold until administration.

USP 795 designates a beyond use date for this preparation not longer than 6 months. Potency testing will be obtained to validate the preparation process.

### **11.2 Dosage and Administration**

At each dosing visit, after a negative pregnancy test is confirmed, the study physician or nurse will provide five daily vaginal suppositories. During that visit, the subjects will be trained in the vaginal insertion of Artesunate suppositories followed by a tampon, and instructed to administer all daily doses at home at bedtime.

The first 3 study subjects (healthy volunteers with CIN2/3) will receive five (5) daily suppositories that contain 50 mg Artesunate. The 50 mg dose (or  $\leq 1\text{mg/kg}$  for subjects weighing 50kg at minimum) is considerably lower than that used when the anal suppository is intended to deliver a systemic dose of drug for malaria – the 50 mg suppository is recommended by WHO for pediatric care. If no local irritation or systemic toxicities observed in the first 3 patients at 50mg, the dosage will escalate to 5 daily doses of 200 mg per day for the remainder of study enrollments (see treatment cohort table).

### **11.3 Accountability Procedures for the Study Investigational Drugs**

Clinical investigators will issue a prescription for each enrolled patient per USP 1168 and State and Federal Law. Buderer Drug Co. will schedule, prepare, package, label and ship clinical trial materials to participating facilities.

The study drug will be kept in the institutional Investigational Drug Pharmacy. Upon receipt of drug orders, and documentation of negative pregnancy test, the pharmacist will dispense enough suppositories for a full cycle (5 days).

#### **11.4 Assessment of Subject Compliance with Self Administration of Artesunate Suppositories**

Eligible patients will have clinic visits scheduled at weeks 0, 2, and 4 for a urine pregnancy test and dosing per their treatment cohort. Once a negative pregnancy test is obtained, the patient will receive 5 doses of Artesunate for the respective treatment cycle. They will receive instructions on how to apply the vaginal suppositories a tampon for medication barrier at bedtime. Patients will be instructed to keep the tampon for the remainder of the night. Before the patient leaves the clinic, the study team will confirm contact information where they can be reached the following week. Patients will document any adverse events, and will undergo a cervix check in clinic when they return for the following Artesunate dosing visit.

**Toxicities and Adverse events**

**Table 5: Solicited General Signs and Symptoms**

Adverse Event	Short Name	Grade 1	Grade 2	Grade 3	Grade 4	Grade 5
Allergic reaction/hypersensitivity (including drug fever)	Allergic reaction	Transient flushing or rash; drug fever <38°C (<100.4°F)	Rash; flushing; urticaria; dyspnea; drug fever ≥38°C (≥100.4°F)	Symptomatic bronchospasm, with or without urticaria; parenteral mediation(s) indicated; allergy-related edema/angioedema; hypotension	Anaphylaxis	Death
Fever (in the absence of neutropenia, where neutropenia is defined as ANC <1.0 x 10  /L)	Fever	38.0-39.0°C (100.4-102.2°F)	>39.0-40.0°C (102.3-104.0°F)	>40.0°C (104.0°F) ≤24 hours	>40.0°C (104.0°F) >24 hours	Death
Cytokine release syndrome/acute infusion reaction	Cytokine release syndrome	Mild reaction; infusion interruption not indicated; intervention not indicated	Requires therapy or infusion interruption but responds promptly to symptomatic treatment (e.g., antihistamines, NSAIDs, narcotics, IV fluids); prophylactic medications indicated for ≤24hrs	Prolonged (i.e., not rapidly responsive to symptomatic medication and/or brief interruption of infusion); recurrence of symptoms following initial improvement; hospitalization indicated for other clinical sequelae (e.g. renal impairment, pulmonary infiltrates)	Life-threatening; pressor or ventilatory support indicated	Death

Nervous system disorder	Head aches	Mild pain	Moderate pain, limiting instrumental ADL	Severe pain, limiting self care, ADL	—	-
Nervous system disorder	Dizziness	Mild unsteadiness or sensation of movement	Moderate unsteadiness or sensation of movement, limiting instrumental ADL	Severe unsteadiness or sensation of movement; limiting self care ADL	—	-
Ear and labyrinth disorder	Tinnitus	Mild symptom intervention not indicated	Moderate symptoms, limiting instrumental ADL	Severe symptoms, limiting self care ADL	-	-

Patients will be monitored throughout the study for both known potential risks and for unexpected risks. During office visits, patients will be monitored specifically for any signs of:

- Symptoms of itching, burning, pain, warmth, or tenesmus
- Signs of skin breakdown including erythema, blistering, desquamation, ulceration or bleeding
- Neurologic symptoms
- Unexpected adverse events

Subjects will be given diary cards to record local and general signs and symptoms most likely to occur between office visits. The diary cards will be collected, signs and symptoms verified, and inserted into the CRF at each subsequent visit.

Subjects who become pregnant during study will be required to discontinue the use of suppositories. Subjects removed from the study will be replaced in the treatment group. Although not considered an adverse event, pregnancy will be reported in the same way. Whenever possible, a pregnancy should be followed to term, and the status of mother and child reported. The Pregnancy Notification form will be sent by sites to the study PI ([name]) and to the sponsor (Frantz Viral Therapeutics) within 48 hours of discovery. Whenever possible, the Follow-up Pregnancy Outcome Form will be filled after delivery.

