**Objectives**

Primary Objective:

- To determine and evaluate the safety, tolerability, and feasibility of intra-vaginal administration of Artesunate, administered via vaginal suppository, in healthy women with cervical intraepithelial neoplasia (CIN2/3)

Secondary and Exploratory Objectives:

- To measure the effect of intra-vaginal topical Artesunate administration on histology, based on the regression of CIN2/3 at study week 15, assessed as either CIN1 or no CIN lesion detected by colposcopy/biopsy and cytology.
- To evaluate clearance of HPV as assessed by Hybrid Capture 2 DNA testing of cytologic specimens
- To evaluate the local tissue immune response
- To correlate measures of immune response with clinical response

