### 11.5 Management of Toxicities

All local reactions will be considered causally related to administration of the suppositories. Causality of all other adverse events will be assessed individually. We will follow up subjects with non-serious adverse events until symptoms end. Those with

related serious adverse events will be followed until resolved, until no further improvement is expected, until a non-study antitumor therapy is initiated, or for 30 days after last study treatment, whichever comes first (with the exception of neuropathy, which must be followed until resolution to  $\leq$  grade 1 or until stable for 60 days).

Outcome will be assessed as

- 1=Recovered
- 2=Recovered with sequelae
- 3=Ongoing at subject study conclusion
- 4=Died
- 5=Unknown

Any serious study events that are unexpected and related to the study drug or procedure occurring during the period starting from day of administration of the first dose of Artesunate suppository to each subject and ending at the last study visit for that subject (i.e., scheduled LEEP or cone excisional biopsy procedure), will be reported by the principal investigator.

Subjects who become pregnant during study will be required to discontinue drug. Subjects removed from the study prior to week 15 will be replaced in the dose cohort. Although not considered an adverse event, pregnancy will be reported in the same way. Whenever possible, a pregnancy should be followed to term, and the status of mother and child reported. The Pregnancy Notification form will be sent by sites to the study sponsor ([name]) within 48 hours of discovery. Whenever possible, the Follow-up Pregnancy Outcome Form will be filled after delivery.

Significant local inflammation will be treated symptomatically with cold packs and oral analgesics. Local infection or ulceration will be treated with routine wound care and antibiotics if necessary.

Subjects will be given diary cards to record local and general signs and symptoms most likely to occur at home. The diary cards will be collected, signs and symptoms verified, and inserted into the CRF at each subsequent visit. Subjects will be monitored at regular intervals to ensure that all adverse events are recognized, documented, and treated. Patients will be educated to contact medical staff should they feel that an adverse event has occurred at a time when they are not scheduled for follow-up monitoring and will have access to medical staff to follow up on any such concerns.

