### **13.0 SUBJECT COMPLETION/DROPOUT**

#### **13.1 Definition of a Dropout**

A dropout is defined as any subject who did not come back for at least week 15 visit foreseen in the protocol. A subject who returns for the concluding visit foreseen in the protocol is considered to have completed the study participation. Dropouts will be replaced to reach the target enrollment.

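### The protocol text makes no provision for recording doses taken at home, and Section 12.1 sets no minimum exposure, so under-dosed women can count as DLT-free in the escalation decision

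*Combined protocol and SAP*

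**What the plan says.** Section 11.2 has women "instructed to administer all daily doses at home at bedtime"; Section 10.3 has the first suppository inserted in clinic. On either reading at least four of the five doses in each cycle are taken unobserved, and Section 10.2 lets the last four of the first cycle spread over 4 days to 2 weeks.

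The places where a home dose might be captured are these:

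- Section 11.4, whose heading promises an assessment of compliance, describes a pregnancy test, the supply of five doses, instructions and contact details. After that, "Patients will document any adverse events, and will undergo a cervix check in clinic when they return for the following Artesunate dosing visit".
- The text after Table 5 says of the diary: "Subjects will be given diary cards to record local and general signs and symptoms most likely to occur between office visits". Section 11.5 repeats it: "Subjects will be given diary cards to record local and general signs and symptoms most likely to occur at home". Neither mentions doses.
- Section 11.3 has the pharmacy release one five-day cycle at a time. It asks for no return or count of unused units.
- Table 3 schedules dosing visits and diary collection but no dose check.

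Section 12.1 then bases escalation on the number of women with a DLT among 9, or 12 after an expansion by three. The count is read at the cervix check that follows dosing, with no condition on doses taken. Section 13.1 defines who is replaced by attendance alone: "A dropout is defined as any subject who did not come back for at least week 15 visit foreseen in the protocol". The synopsis lists feasibility among the primary aims ("To determine and evaluate the safety, tolerability, and feasibility of intra-vaginal administration of Artesunate"), but Section 7.1 defines no outcome for it.

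**The concern.** Safety and tolerability drive the primary decision here, and skipped doses are not neutral for that decision. A woman who finds the suppository uncomfortable has a reason to stop using it, and stopping may lower her chance of a DLT. If nobody knows that she stopped, she enters the count as a woman who took the regimen without a DLT. Where under-dosing lowers DLT risk, the error runs one way, towards escalating.

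Two further things depend on dose dates. Section 12.1 times the DLT assessment from the final suppository, and Section 11.7 records adverse events until 30 days after final treatment. With up to two weeks allowed for four doses, that anchor date cannot be fixed from the dispensing date. Cohorts II to IV also share one dose and differ only in number of cycles, so both the comparison between them and the choice of a level for expansion lean on exposure that is known only as cycles dispensed.

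**Working it through.** **Tracing one woman through the text.** In Cohort II she inserts the first suppository in clinic, uses none at home because of non-allergic discomfort below grade 3, and attends the cervix check. Under Section 11.8 she has no DLT. Under Section 12.1 she is one of the nine without a DLT. If she returns at week 15 she is not a dropout under Section 13.1. No step identifies her as under-dosed.

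**Reproducing the stated figure.** Inputs from Section 12.1: 9 women, 3 more if exactly one has a DLT, escalation if the three have none, true DLT rate 30%, stated probability below 9%, maximum 39.

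- Rule as written: 0.7^9 + 9 × 0.3 × 0.7^8 × 0.7^3 = 0.0404 + 0.0534 = 0.0937, or 9.4%.
- At most one DLT in 12: 0.7^12 + 12 × 0.3 × 0.7^11 = 0.0850, or 8.5%. This variant meets the stated bound and may be its source.
- Maximum for escalation: 3 + 3 × 12 = 39, as stated.

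Both probabilities give every counted woman the full 30% risk.

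**Letting some women be under-dosed.** Assumptions, since the documents give no adherence rate: k of the first 9 are under-dosed with DLT rate q; the other 9 − k and any three added women have rate 0.3.

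- No DLT in 9: A = 0.7^(9−k) × (1−q)^k
- Exactly one: B = (9−k) × 0.3 × 0.7^(8−k) × (1−q)^k + k × q × (1−q)^(k−1) × 0.7^(9−k)
- Chance of passing: A + B × 0.7^3

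For k = 1, q = 0: 0.0576 + 0.1977 × 0.343 = 0.1254. For k = 3, q = 0.15: 0.0723 + 0.2240 × 0.343 = 0.1491.

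| Under-dosed of first 9 | q = 15% | q = 10% | q = 0 |
|---|---|---|---|
| 0 | 9.4% | 9.4% | 9.4% |
| 1 | 11.0% | 11.5% | 12.5% |
| 2 | 12.8% | 14.0% | 16.7% |
| 3 | 14.9% | 17.1% | 22.1% |

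**What zero DLTs would show.** The one-sided 95% upper limit after 0 of n is 1 − 0.05^(1/n): 28.3% for n = 9, and 39.3% if only 6 of the 9 were fully dosed.

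**Does replacing under-dosed women restore 9.4%?** Only if skipping is unrelated to DLT risk. Suppose instead that one third of the women who would have a DLT stop early and escape it, in the first nine and the added three alike.

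- Unreplaced, the observed rate is 0.3 × 2/3 = 0.20, and the rule passes with probability 0.8^9 + 9 × 0.2 × 0.8^11 = 28.9%.
- With those women replaced, the rate among evaluable women is 0.20 / (0.20 + 0.70) = 0.222, and the probability is 0.778^9 + 9 × 0.222 × 0.778^11 = 23.0%.

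Replacement helps but leaves most of the bias.

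**The case against.** The other side has several good points.

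- **The forms are not in the documents.** The diary card and case report form may have a dose field, and Section 10.3 sends all clinically relevant data to the patient file. A reader might infer that doses are never recorded; the documents support only that the protocol text does not provide for it. This stands.
- **Week 15 is not the escalation point.** A reader might infer that the attendance-based dropout definition puts under-dosed women into the escalation count. It governs replacement. They enter because Section 12.1 has no evaluability rule based on doses. This stands.
- **A missed cycle can show.** Cycles 2 and 3 are handed out at separate visits, so a cycle lost with its visit appears in the dispensing record. It is therefore too strong to say that the cohorts cannot be shown to differ at all. Use within a dispensed cycle remains unknown.
- **Discomfort is still reported.** Symptoms are collected on the diary, local reactions are treated as related (Section 11.5), and toxicities are tabulated (Section 12.4). For the run-in, Sections 3.2 and 11.2 also make escalation depend on the absence of adverse events or local irritation, so no run-in figure is given here. This stands, but in the 200 mg cohorts the Section 12.1 count still turns on DLTs alone.
- **Zero risk is an extreme.** Every enrolled woman receives at least one suppository, and a grade 2 allergic reaction is a DLT. The q = 0 column is therefore an upper end for each assumed number under-dosed.
- **Feasibility is not without data.** Attendance, dispensing and dropout reasons are available. What is missing is doses taken and a defined feasibility outcome.

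**Conclusion.** The gap is real and should be fixed. The protocol text provides for neither a record of home doses nor a dose-based DLT-evaluable set, so applied as written the escalation rule can score non-use as absence of toxicity, and the date that anchors the DLT window is undocumented. Dose histories cannot be reliably rebuilt afterwards.

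The size is uncertain. From 9.4% under full exposure, the chance of passing a level with a 30% DLT rate moves to between 11.0% and 22.1% when 1 to 3 of the first 9 are under-dosed. Both that number and the residual DLT rate of 0 to 15% are assumptions. The figures show direction and plausible scale; they do not estimate what will happen in this trial.

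**What to change.** 1. Add to the existing diary card the date of each suppository, or that it was not taken and why. Count returned units at visits already scheduled.
2. In Section 12.1, prespecify the DLT-evaluable set: any woman with a DLT, plus women who took at least a share of their cohort's doses, set in advance by the protocol team, and had the post-dose cervix check. Replace non-evaluable women for the escalation count only, and keep them in all safety tables.
3. Because replacement alone does not remove the bias if the least tolerant women stop, tabulate by cohort the doses taken and the women who stopped or skipped doses because of symptoms. Put that table before each escalation decision and report it as the feasibility and tolerability outcome.

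While Section 12.1 is open, state the formula behind the figure of less than 9%, or reword it, since the rule as written gives 9.4%.

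The cost is a line on a card already issued and collected, a count at existing visits, a short addition to Section 12.1 and one table. The downside is a few replacements if adherence is poor.
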